Title of Study: "Randomized Controlled Trial of PTNS versus Sham Efficacy in Treatment of Bladder Pain Syndrome."

Principal Investigator: [name]

Study Number: s15-01447

• **PURPOSE OF THE STUDY AND BACKGROUND –**

- Our primary aim in this pilot study is to evaluate the efficacy of the systematic effects of posterior tibial nerve stimulation (PTNS) treatment compared to an inactive sham intervention in female subjects with interstitial cystitis/bladder pain syndrome (IC/BPS) in an intent-to-treat analysis. Our primary outcome measure will be the Patient Global Impression of Improvement (PGI-I) a single item questionnaire assessing overall impression of improvement over time at the initial 12 weeks endpoint.
- Our secondary outcomes will include change from baseline in SF-12 quality of life scores, Visual Analog Scale (VAS) and O'Leary –Sant pain scores at 12 weeks To confirm the validity of the sham, subjects will be asked to identify which intervention they believed they received during the study at study conclusion. Additionally subjects will be presented with OAB-Q short forms. This will allow for evaluation of subjects with concomitant overactive bladder and painful bladder syndrome characteristics.
- We hypothesize that subjects randomized to the PTNS arm will demonstrate a greater improvement in both pain and quality of life scores, when compared with subjects who are randomized to the sham arm. Additionally, we hypothesize that the validity of the inactive sham intervention will be appropriately confirmed in our study population.

- **Background:**
- Bladder Pain Syndrome (BPS), which includes the sub-variant of interstitial cystitis (IC), is defined as "an unpleasant sensation (pain, pressure, discomfort) perceived to be related

to the urinary bladder, associated with lower urinary tract symptoms of more than six weeks duration, in the absence of infection or other identifiable causes”(1).

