- On-site training of investigators and research staff will include a study protocol lecture, demonstration of blinding apparatus setup, use of a standard PTNS system (needle, grounding pad and energy source) according to manufacturer instructions for use, and use of a TENS unit and placebo needles (for sham subjects). Subjects and study coordinators who will administer questionnaires will be blinded to the assigned treatment intervention throughout the trial. All subjects will be randomized 1:1 at the first intervention visit to PTNS or sham using a random block design. During the intervention session subjects will be in a comfortable seated position and lower extremities will be blocked and draped from view. All subjects will have three electrode pads placed to standardize the perception of the intervention between the 2 treatment arms. Next, instead of the inactive grounding pad used on the PTNS leg, the sham subjects will have an active adhesive pad placed on the bottom of the foot just below the smallest toe. This spot was chosen, as described in sham validation (17) since it is not part of the acupressure or acupuncture nerve pathway connected to the bladder, pelvis or any major organs. All subjects will be informed that they may or may not feel a sensory stimulus effect on their lower extremities as a result of the intervention. Subjects in both study groups will receive 12 weekly 30-minute intervention sessions and will be queried about adverse events. Evaluation of primary end point will be done on a weekly basis. Every two weeks the individual response to this parameter will be

assessed. Additionally, the overall change in primary endpoint will be evaluated at week 12. The secondary endpoints will be evaluated at week 12 as well. There will be a debriefing at week 12 after the study has been completed, to reveal to the subject which arm they were in.

- **PTNS group:**

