- Sessions for both groups will be performed once per week for 30 minutes. The total treatment period will be 12 weeks. All patients will undergo thorough evaluation for bladder pain through a detailed history and physical exam (both general physical and gynecologic). Baseline characteristics will be collected. At the baseline of the study and at completion of the 12-week treatment all patients still enrolled will be asked to fill out general and disease-specific pain and quality of life questionnaires. We will use VAS and the O'Leary-Sant scores to determine pain intensity, location of pain and associated symptoms. The OAB-Q will be used to identify characteristic features of associated bladder pain and OAB symptoms. The SF-12 scale will be used to evaluate quality of life of each subject at the three analysis intervals. Patient Global Impression of Improvement (PGI-I), a single item questionnaire assessing overall impression of improvement over time, will be administered at the initial visit and each visit thereafter up through the 12 weeks endpoint. This will allow us to assess progress of the primary end-point week-by-week and overall from baseline to end of treatment. Additionally we will perform an analysis of analgesia use and other past treatments used for pain in this population.
- Full disclosure of research proposal and description of the two possible arms of randomization will be conducted with all participants in the form of both written and verbal communication. Our goal is to conduct this study at NYU Hospital and this will ensure a wide catchment area, including women of various ages, ethnic groups and socioeconomic backgrounds. No subject will be excluded based on race, age or ethnicity. Subjects will also have opportunities throughout the trial to voice any concerns regarding the study and all human subjects will be protected from foreseeable research risks, as this trial will undergo IRB approval prior to initial execution.

- **Data Analysis and Data Monitoring.**

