- The interventions applied in this study represent minimal risks to our subjects. Therefore a data monitoring committee will not be employed to monitor subject safety. The twelve (12) 30-minute PTNS sessions makes up the interventional portion of this study. There are no expected complications from a twelve (12) week PTNS treatment regimen beyond mild patient discomfort or mild bruising at the needle insertion site. The data that will be collected as part of the data safety monitoring plan will revolve around the PTNS and sham treatment sessions and patient experience with the PTNS and sham treatments. All data gathered beyond the PTNS vs Sham trial is purely observational. Patients

requesting to be removed from the study early and patient reports of pain associated with the treatments will be taken note of. [name] will be responsible for monitoring the data. [name] is the primary contact for subjects and thus she will be aware of unanticipated problems and any adverse events as they occur. After each 10 patients are enrolled, [name] and [name] will review any adverse/unanticipated events or patients requesting early trial removal. Events causing serious injury would be unexpected and will be reported to the IRB. This is a relatively small study and thus there is no planned interval analysis of the data.

- **Data Storage and Confidentiality.** The research data will be stored in a database that is password protected in the NYU network drive. The patient data will be entered into a coded database for the purposes of analysis. [name] and [name] will have access to the decoding key for the purposes of collecting the follow up questionnaires and entering this data into the database.
- **RISK/BENEFIT ASSESSMENT**
 - **Risk.** The additional risk assumed by the subjects due to participating in the PTNS/Sham trial stems from the fact that they will potentially be randomized to the inactive sham treatment arm. The risks of PTNS in general are described above and again are uncommon (1-2%). The sham arm will hold similar yet likely even less common risks, as there will still be an initial needle prick using the sham needle but no puncture of the skin and needle will be retracted into the sham needle sheath. The possibility and nature of risk is thoroughly explained in the consent form that they are given prior to agreeing to study participation.

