 - **Protection against Risks.** In an effort to reduce risk and discomfort to the patient, the study needle, grounding pad and energy source will all be placed and controlled by an attending or fellow from the Female Pelvic Medicine and Reconstructive Surgery division of the Urology department. Additionally, questionnaires are as short as possible and a physician from the urology department will be available to answer questions at all times for the patient during their 12 sessions should the device or needle cause them discomfort or should they have any concern. Should patients desire to terminate the PTNS trial at any time, someone from the urology department will be made available to them to remove the needle and disconnect the device. The criteria for

termination of the trial will be patient inability to sustain treatment sessions or patient request to be removed.

- **Potential Benefits to the Subjects.** There are potential individual benefits to the subjects participating in this trial. The possible benefit would be improvement in bladder pain symptoms. This potential benefit could be greater in the PTNS versus sham group, however patients are aware of this prior to consenting to the study.
- **SUBJECT IDENTIFICATION, RECRUITMENT AND CONSENT/ASSENT**
 - **Method of subject Identification and Recruitment.** Subjects presenting to NYU Urology Associates, Female Pelvic Medicine and Reconstructive Surgery (FPMRS) division, who meet the inclusion criteria, will be recruited to participate in this study during the enrollment period. Drs. [name], [name], [name], [name] [name], [name] and [name] comprise the FPMRS division. Subjects will be identified by the treating physician and the treating physician will introduce the study and request permission for another member of the study team to approach the patient. In order to reduce undue influence over the patients, the primary treating physician will not recruit the subject to participate in the study. Recruiting will be performed either by a Fellow or another attending of Female Pelvic Medicine and Reconstructive Surgery division. Subjects will be assured that participation is completely voluntary and declining will not influence their care.

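### Week-12 questionnaires go only to women who remain enrolled; if stopping sessions ends enrolment, the 12-week intent-to-treat comparison will lack their outcomes

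*Combined protocol and SAP*

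**What the plan says.** The Purpose section sets the comparison "in female subjects with interstitial cystitis/bladder pain syndrome (IC/BPS) in an intent-to-treat analysis". PGI-I at 12 weeks is primary; changes in SF-12, VAS and O'Leary-Sant at 12 weeks are secondary.

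The assessments paragraph of Methods and Procedures says who is asked. For the end of treatment it reads: "12-week treatment all patients still enrolled will be asked to fill out general and disease-specific pain and quality of life questionnaires". PGI-I "will be administered at the initial visit and each visit thereafter up through the 12 weeks endpoint", and earlier in the same section: "Evaluation of primary end point will be done on a weekly basis". SF-12 is to "evaluate quality of life of each subject at the three analysis intervals"; the three intervals are not defined.

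Protection against Risks has two relevant sentences. One, opening "Should patients desire to terminate the PTNS trial at any time", provides for removing the needle and disconnecting the device. The next gives two grounds for termination: a patient who cannot keep up the sessions, and a patient who asks to leave.

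Four other places bear on follow-up:

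- Data Analysis and Data Monitoring: requests for early removal are noted, and after every 10 enrolments two staff members "will review any adverse/unanticipated events or patients requesting early trial removal".
- Data Storage and Confidentiality: staff hold the decoding key partly in order to collect follow-up questionnaires.
- Process of Consent: surveys are listed at baseline, at each visit and in a 13th week.
- Debriefing: "There will be a debriefing at week 12 after the study has been completed"; Debriefing Procedures places it after the subject's questionnaires are complete.

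**The concern.** An intent-to-treat comparison at 12 weeks aims at the difference between all randomised women in their assigned arms, whether or not they continued sessions. That needs week-12 answers from women who stopped, or a defensible way of standing in for them. The protocol does not clearly ask these women for answers, and it gives no rule for missing values.

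An analysis can be rewritten later, but a week-12 answer that was never requested cannot be recovered. If women stop for reasons linked to how they are doing, and this differs between arms, the women observed at week 12 are no longer comparable across arms. The distortion could favour either PTNS or sham.

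**Working it through.** **Plan's own figure.** There is none to reproduce. Enrolment of 100 (Number of subjects) is stated without a derivation, and no dropout or response rate is given for this trial. The 71% PTNS adherence quoted in the background comes from a cost study in overactive bladder.

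**Step 1: what a woman who stops would contribute, under each reading of the enrolment wording.** The end-of-treatment questionnaires are taken to be the four instruments that the same paragraph goes on to name.

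| Outcome | Scheduled | If stopping ends enrolment | If she remains enrolled |
|---|---|---|---|
| PGI-I (primary) | every visit to week 12 | earlier weekly values only | sought if she attends or is contacted |
| VAS, O'Leary-Sant, OAB-Q | baseline and end of treatment | nothing after baseline | asked at week 12 |
| SF-12 | each subject, three undefined intervals | unclear | asked at week 12 |

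The follow-up questionnaires, 13th-week survey and debriefing favour the right-hand column. None of them mentions women who stopped, so none settles the matter.

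**Step 2: illustration of size.** Everything here is assumed except 50 per arm (100 randomised 1:1): PGI-I as improved yes/no, all rates, and analysis of observed women only. Let p be the true proportion improved, and dr and dn the loss among improved and non-improved women.

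Observed rate = p(1−dr) / [p(1−dr) + (1−p)(1−dn)]

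Take p = 0.30 in both arms (no true effect) and dr = 0. Bias is PTNS minus sham, in percentage points.

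| dn PTNS / sham | Women lost of 50 | Observed rates | Bias |
|---|---|---|---|
| 10% / 20% | 3.5 / 7 | 32.3 / 34.9 | −2.6 |
| 10% / 30% | 3.5 / 10.5 | 32.3 / 38.0 | −5.7 |
| 10% / 40% (extreme) | 3.5 / 14 | 32.3 / 41.7 | −9.4 |
| 20% / 10% | 7 / 3.5 | 34.9 / 32.3 | +2.6 |
| 30% / 10% | 10.5 / 3.5 | 38.0 / 32.3 | +5.7 |
| 20% / 20% | 7 / 7 | 34.9 / 34.9 | 0 |

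The zero in the last row needs no true effect. With true rates of 50% and 30%, the same equal loss gives 55.6 − 34.9 = 20.7 against 20. Loss unrelated to outcome within each arm (dr = dn) returns p exactly.

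**Step 3: what each remedy does to the 10%/40% and 30%/10% cases.**

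- *Reaching a random share r of leavers* replaces dn by dn(1−r). At r = 0.5, bias is −3.8 and +2.4; at r = 0.8, −1.4 and +0.9.
- *Conditioning on an earlier PGI-I value X* that agrees with week-12 status Y 80% of the time: estimate = Σ P(X=x)·P(Y=1 | X=x, observed). For dn = 0.4 this is 0.38×0.741 + 0.62×0.152 = 0.375. For dn = 0.1 it is 0.38×0.656 + 0.62×0.106 = 0.315. Bias is −6.0, and +3.7 in the other case. It is 0 if stopping depends only on X.
- *Carrying the earlier value forward* adds 0.7×dn×0.2 to 0.30: 0.314 against 0.356, a bias of −4.2, and +2.8 in the other case. If stopping depends only on X (loss among women with X = 0), the estimate is 0.30 − 0.06×loss: 0.294 against 0.276, a bias of +1.8, and −1.2 in the other case.
- *Counting missing as not improved* gives 0 in every row of the table, because there only non-improved women leave. If stopping depends only on X, it gives the same +1.8 and −1.2 as carrying forward.

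**Step 4: no assumption about why women leave.** Each missing woman widens the possible range of the arm difference by 1/50 = 2 points. Five missing per arm gives 10/50 = 20 points.

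**The case against.** The strongest reply is that the gap depends on one reading. The termination sentence sits under risk protection, directly after needle removal, and may mean no more than ending treatment. If women who stop remain enrolled, the existing wording already covers their end-of-treatment questionnaires. The follow-up questionnaires, the 13th-week survey (beyond the 12 sessions) and the debriefing all lean that way. The consent pages are not in the text reviewed and may contain terms for later contact. All of this stands: what is shown is an ambiguity.

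The reply is also right that the figures carry little evidential weight. Every rate is assumed, no observed-women analysis is specified, and the intent-to-treat statement points away from one. Counting missing as not improved would remove all the illustrated no-effect bias without further data collection. That result, however, requires that only non-improved women leave, which nobody can know in advance.

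Three stronger inferences are tempting, and the documents support none of them:

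- *That the protocol excludes women who stop, or contradicts intent-to-treat.* It does not say that stopping ends enrolment. Intent-to-treat concerns analysis by assigned arm and does not fail merely because some outcomes are missing.
- *That the primary outcome would be lost.* Weekly PGI-I leaves earlier values, which partly protect it.
- *That the result will be off by some stated amount, or in PTNS's favour.* Nothing in the protocol establishes differential dropout or its direction.

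**Conclusion.** The point holds as a limited one. The protocol does not assure week-12 outcomes from women who stop sessions, and on one plausible reading it would not seek them. VAS, O'Leary-Sant and OAB-Q are most exposed because they have no scheduled intermediate values. PGI-I is partly protected, but no rule says how its earlier values would be used. SF-12 cannot be judged.

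Bias in the comparison of observed women requires that stopping be related to outcome; differing patterns by arm then push it in either direction. Its size for this trial cannot be derived, and the figures of roughly 3 to 9 points are illustration only. The change is worth making because the data are unrecoverable and the remedy is inexpensive. Confidence is medium, since the investigators may already intend full follow-up.

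**What to change.** - **Methods and Procedures, assessments paragraph:** replace the restriction to patients who remain enrolled with all randomised subjects, including those who stop sessions. Seek PGI-I, VAS, O'Leary-Sant, OAB-Q and SF-12 at week 12, in person or remotely, before the arm is revealed, unless consent for data collection is withdrawn.
- **Protection against Risks:** distinguish stopping sessions from leaving data collection, without changing when sessions stop.
- **Analysis:** include all randomised women in their assigned arm. For missing week-12 PGI-I, name a method that conditions on the earlier weekly values, such as a repeated-measures model or multiple imputation by arm. Do not carry the last value forward: in the illustration it was less biased when stopping depended on week-12 status, but it stayed biased when stopping depended only on recorded values, where conditioning is not.
- **Sensitivity and reporting:** count missing as not improved as a sensitivity analysis, and report missingness and reasons by arm.

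The cost is rewording two sections, some remote questionnaire contacts and one extra analysis. Some week-12 values will be off treatment. They belong to the intent-to-treat target, though the estimated effect may be smaller than among women who complete treatment.

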could be undertaken. The estimated cost of PTNS is approximately \$1,800 for 12 sessions, which is the approved number of sessions currently outlined in the FDA usage of PTNS for other pelvic floor disorders. In contrast, the cost of sacral nerve stimulation is significantly higher. A recent study comparing costs of neuromodulation therapies for OAB revealed that cost after completing initial therapy with PTNS was \$4867.00 while completion of SNM implantation and initial treatment cost an average of \$24,342.00. Additionally, it was found that both methods had high levels of adherence, reaching 71% and 90%, respectively, however data revealed an incremental cost-effectiveness ratio of \$99,872 in favor of PTNS (22). The proposed study can provide critical data to build cost-effectiveness models that will help answer important questions as health care resources become more limited. PTNS, if proven effective for treatment of bladder pain syndromes, could improve quality of life for many of the approximately 7 million women in the United States who are affected by bladder pain. Cost-effectiveness data may lead to savings that are significant to the healthcare system. A longer term look at the persistence of treatment will factor into this model as many patients with bladder pain are involved in a clinical paradigm, which includes multiple office and emergency room visits due to titration of analgesic interventions, etc. If PTNS proves to be an efficacious and has medium and long-term benefit for the treatment for BPS, this could result in even more cost savings for the healthcare system and the patient. This study is the first step to an accurate cost-analysis study in BPS.

- **Study Design:** This is a prospective, single center, double-blind, randomized, controlled trial comparing the efficacy of percutaneous tibial nerve stimulation to sham in the treatment of Bladder Pain Syndrome/Interstitial Cystitis (BPS/IC) through 12 weeks of therapy.

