- Botox use in pelvic floor muscles within the last year
- Current urinary or vaginal infections
- Current use of Interstim device
- History of a cardiac pacemaker
- Diagnosis of neuropathy

- **Vulnerable Subjects:** No vulnerable subject populations based on federal regulations are included in this trial. Children and fetuses are not affected by this disease, pregnant women are not PTNS candidates, and prisoners are not treated at the study site. The elderly are a potential, albeit likely small proportion of the patients with the diagnosis of BPS, thus they need to be included in our study population to make the results useful in clinical practice. They will be included in our study; however those who are no longer able to provide consent for themselves will be excluded.

- **METHODS AND PROCEDURES**

- **Methods and Procedures:**

- **Approach:**

- All patients seen at New York University Center for Female Pelvic Medicine to in the Department of Urology who suffer from BPS/IC, as defined above, will be offered

participation in this prospective randomized controlled study.

- Inclusion criteria will include: women \geq 18 years old with visual analog scale > 5 , cessation of all analgesics or other medication for pain for at least 2 weeks prior the PTNS intervention, discontinuation of any other electrical stimulation methods 3 months prior to PTNS intervention, capable of giving informed consent, ambulatory, capable and willing to follow all study-relation procedures.
- Exclusion criteria will include patients pregnant or planning to become pregnant during the study duration, Botox use in pelvic floor muscles within the last year, current urinary or vaginal infections, current use of Interstim, history of a cardiac pacemaker, diagnosis of neuropathy.
- Randomization will be carried out using computer-generated random allocations. A computerized random number generator will be used to generate a number 1-100. All odd numbers will be randomized to PTNS arm and all even numbers will be randomized to sham arm. This number will be generated by a co-investigator who is not involved in the consent process. He or she will provide an envelope revealing the randomization result to the investigator who is consenting the subject. Institutional Review Board approval from the NYU IRB will be obtained prior to starting the study.

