- The medial aspect of the lower extremity will be palpated and a needle insertion site will be identified approximately 5 cm cephalad from the medial malleolus and slightly posterior to the tibia. Between the posterior margin of the tibia and the soleus muscle, a 34-gauge acupuncture-like needle will be inserted approximately 3–4 cm deep to the tibial nerve. An adhesive grounding pad will be placed on the bottom of the foot just below the smallest toe. An inactive adhesive grounding pad will be placed on the top of the foot just above the small toe to be consistent with the sham pad placement. The needle and grounding pad will be connected to the stimulator and the stimulation will be increased from 0 to 10 mA as tolerated. Flexion of the greater toe and sensory stimulation in the bottom of the foot will be used to confirm proper needle placement. The needle will be taped in place. The electrical current will be set at an intensity that is well tolerated by the subject and the mA will be recorded on a subject report form. A 30-minute stimulation session will be given at 20 Hz. At the end of the procedure, the needle and grounding pad will be removed and discarded.

- **Sham group:**

- The medial aspect of the lower extremity will be palpated and a needle insertion site will be identified approximately 5 cm cephalad from the medial malleolus and slightly posterior to the tibia. Between the posterior margin of the tibia and the soleus muscle a sham needle will be used at the tibial nerve insertion site. This will stimulate needle placement without puncturing the skin. The needle will be taped in place, similar to the PTNS procedure. The “grounding pad” from the TENS unit device will be placed on the bottom of the foot just below the smallest toe. Another gel electrode will be placed on the top of the foot just above the small toe for conduction. The TENS electrode will be connected by lead wires to the TENS unit, set at 20 Hz (as in the PTNS group). The TENS unit will then be turned on and the stimulation will be increased to the subject’s first sensory level. At the time the subject senses localized stimulation to either the bottom of the foot or the toe the TENS unit will be left on for a 30 minute test period. The TENS unit will then be removed and the needle will be removed and discarded.

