 - **Process of Consent.** Consent to participate in the study will be performed by one of the physicians in the Female Pelvic Medicine and Reconstructive Surgery division. They are, [name], [name], [name], [name], [name], [name], [name], or [name]. Prior to the consent process a physical exam will need to be performed if there is not one documented from the last three months. At time of the consent process, the PTNS device and characteristics of the treatment sessions will be described to the subjects. It will be made clear to them that the PTNS trial is for research purposes and is not a part of their routine treatment algorithm. The physicians obtaining consent are well trained in the use of PTNS for FDA approved treatment of overactive bladder and will be able to answer general questions about PTNS that the subject may have. The additional time commitment of filling out surveys at baseline, each visit and at the 13th week will be discussed as well

as the commitment to possible randomization to inactive sham treatment arm.

The majority of this patient population are English speaking. Should the subject require a translator, this will be noted on the consent and a signature of the translator will be obtained.

- **Subject Capacity.** Subjects without the capacity to consent for themselves will not be recruited to participate in this study. Any PTNS treatment trial requires that a patient be able to maintain appointments for treatment sessions accurately report on her symptoms associated with BPS/IC.
- **Subject Comprehension.** The PTNS/Sham trial is fairly straightforward. The most difficult thing to describe to patients is the idea of being randomized to PTNS treatment or sham arms for the purpose of assessing PTNS as a viable treatment option for BPS/IC. A physician well trained in symptoms of BPS/IC and the characteristics of PTNS treatment sessions as well as understanding of the PTNS device will be obtaining consent and will be present at the time of treatment sessions. At any point during this process the subject can decline to continue to participate.

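### The trial is labelled double-blind, but arm-aware physicians attend the sessions and nothing limits what they convey to subjects who self-rate the primary outcome

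*Combined protocol and SAP*

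**What the plan says.** Study Design gives the label: "This is a prospective, single center, double-blind, randomized, controlled trial". Methods and Procedures (Approach) says who is covered: "Subjects and study coordinators who will administer questionnaires will be blinded to the assigned treatment intervention throughout the trial". No one else is listed as blinded.

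On who learns the arm, the randomization paragraph of the same section says of the co-investigator who generates the number: "He or she will provide an envelope revealing the randomization result to the investigator who is consenting the subject". Subject Comprehension then describes a physician trained in the condition and with "understanding of the PTNS device will be obtaining consent and will be present at the time of treatment sessions". Protection against Risks adds that "the study needle, grounding pad and energy source will all be placed and controlled by an attending or fellow" of the division.

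On records, the PTNS group description says "the mA will be recorded on a subject report form"; the Sham group description mentions no corresponding entry. Under Data Storage and Confidentiality, two people whose names are removed "will have access to the decoding key for the purposes of collecting the follow up questionnaires and entering this data into the database".

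The primary outcome is the PGI-I, a single self-rated item, given at the initial visit and every later visit up to week 12.

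**The concern.** When the subject scores her own improvement, blinding has to cover what she sees and feels, and also what the people treating her convey. The plan deals with the first in some detail and is silent on the second. Physicians who know the arm meet her at repeated sessions and have to talk to her, because in both arms the current is set from her reports of sensation or tolerance. The Background itself points to a high placebo response in pain syndromes, so expectation is a plausible influence by the protocol's own account.

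If arm-aware physicians are more encouraging towards PTNS subjects, even without meaning to be, the difference goes straight into the PGI-I and looks like efficacy. It cannot be removed at analysis, because the plan collects nothing on what physicians said.

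**Working it through.** **1. Who knows the arm, and who meets the subject.**

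| Person | Knows the arm? | Contact with the subject | Where stated |
|---|---|---|---|
| Subject | No | – | Approach |
| Coordinator giving questionnaires | No | Administers questionnaires | Approach |
| Consenting investigator | Yes, by envelope | Consent, and present at sessions | Approach; Subject Comprehension |
| Operator (attending or fellow) | Yes: real needle and stimulator, or sham needle and TENS unit | Places and controls the device | PTNS group; Sham group; Protection against Risks |

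Two of the three staff roles in the table are arm-aware, and both meet the subject during treatment. Twelve sessions of 30 minutes come to 12 × 0.5 h = 6 h. That is a ceiling on contact, since the text does not say that the physician stays throughout.

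**2. Does any stated safeguard act on this route?** Draped legs, three pads for everyone, a common statement about possible sensation and a sham reported as validated all act on what the subject perceives of the device. Training covers the blinding apparatus, with no mention of what staff may say. The treatment guess comes at study conclusion, so it may detect unblinding but cannot prevent it. Blinded coordinators separate the questionnaire from the operator by person. The text does not say that the operator is out of the room. None of these limits what an arm-aware physician conveys.

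**3. Records.** The current is described as recorded for PTNS only. If the sham form carries no such entry, a coordinator who sees the form can tell the arm. The plan does not say where the form is kept or who may read it.

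**4. Scale, on assumed inputs.** The plan gives no figure to reproduce: it states no test, significance level or expectation effect. It gives 100 subjects (Number of subjects) and 1:1 allocation (Approach), so 50 per arm. Assume no true effect, a two-sided 5% test on an outcome in SD units, and a pure expectation shift of d SD towards PTNS.

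SE = √(2/50) = 0.2, and P(falsely favouring PTNS) = Φ(d/0.2 − 1.96).

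- d = 0: Φ(−1.96) = 2.5%
- d = 0.1: Φ(0.5 − 1.96) = Φ(−1.46) = 7.2%
- d = 0.2: Φ(1.0 − 1.96) = Φ(−0.96) = 16.9%
- d = 0.3: Φ(1.5 − 1.96) = Φ(−0.46) = 32.3%

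If the PGI-I is instead analysed as responder or not, with an assumed sham response of 20–40% and a shift of δ, the corresponding argument of Φ is [δ − 1.96√(2p̄(1 − p̄)/50)] / √([p₁(1 − p₁) + p₀(1 − p₀)]/50). For p₀ = 0.40 and δ = 0.10 this is (0.100 − 1.96 × 0.0995)/0.0990 = −0.96, or 16.9%. Across the range, shifts of 5, 10 and 15 points give 7–9%, 17–21% and 32–39%. The two scales tell the same story.

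**The case against.** The strongest reply is that an unblinded operator is hard to avoid when one arm has a needle through the skin and the other does not. The plan says openly who is blinded, and it puts the questionnaires in the hands of blinded coordinators. Session length is the same in both arms, the subject's view is blocked, and debriefing follows all questionnaires. The size of any expectation effect is nowhere given and could be near zero.

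Much of this stands. The operator's knowledge is not itself a defect, and the label alone would be a matter of wording. What remains is that nothing governs the arm-aware physicians' conduct or their presence when the outcome is rated, and both can be governed cheaply.

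A reader might infer more than the text supports:

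- **That questionnaires are handled by unblinded physicians.** Administration is assigned to blinded coordinators; only timing and location are left open.
- **That the decoding key exposes the allocation to those entering data.** It belongs to a coded database described under confidentiality and may only link codes to identities. The holders' names are removed, so nothing can be concluded about who they are.
- **That the physician available for questions during the sessions knows the arm.** Protection against Risks does not say so, nor that this person is the operator.
- **That the report form does reveal the arm.** Silence about a sham entry does not show that none is made, and the plan does not say that coordinators see the form.

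**Conclusion.** The point holds as a gap in safeguards and an imprecise label. As written, the consenting investigator and the operator know the arm and meet the subject at treatment sessions, the primary outcome is her own rating, and no rule limits what they convey or keeps them away while she rates. The possible leak through the session form is a secondary point and rests on inference.

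The size of the bias is unknown. The range of 2.5% to 32% for shifts of 0 to 0.3 SD shows sensitivity only; it depends on the assumed shift, the assumed test and 50 analysed per arm. The documents do not support saying that a positive result would be uninterpretable, because the masking and the treatment guess retain value. The change is worth making before enrolment because it is cheap and cannot be applied once subjects have rated.

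**What to change.** 1. **Methods and Procedures (Approach).** Have operators and any arm-aware physician use one fixed neutral script in both arms. They should not comment on expected or observed response, but should still answer safety and comfort concerns. Blinded coordinators hand out and collect the PGI-I, the week-12 questionnaires and the treatment guess with arm-aware physicians absent. Time the final rating to cover the end of treatment and to precede debriefing; a rule of rating before every session could miss the effect of the last one. Process of Consent mentions surveys at the 13th week, while Approach and Debriefing Procedures place debriefing at week 12. Reconcile these so that no survey follows unblinding.
2. **PTNS group and Sham group.** Record the stimulation setting in both arms on a same-format session form that coordinators and data-entry staff do not see.
3. **Data Storage and Confidentiality.** State that the decoding key excludes the allocation, or that those collecting and entering questionnaires cannot see the allocation.
4. **Study Design.** Describe the trial as blinded for subjects and questionnaire administrators, with the operator and consenting physician not blinded.

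The cost is protocol wording, a short script and a revised form. The coordinators are already in the plan, so no staff are added. The downside is slightly more choreography at visits and a less favourable blinding label.
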